#### 9.4.3 Safety Analyses

Safety and tolerability will be assessed in terms of DLTs, AEs/SAEs, vital signs, clinical chemistry/haematology parameters, physical examination findings, and ECG data. These

variables will be collected for all participants. All safety analyses will be performed on the Safety Analysis Set.

Medical Dictionary for Regulatory Activities (MedDRA; latest version) will be used to code AEs. AEs will be graded according to the National Cancer Institute CTCAE Version 5.0. The number of participants in each dose regimen experiencing each AE will be summarised by MedDRA system organ class and preferred term. The number and percentage of participants with AEs in different categories (e.g., causally related, CTCAE Grade  $\geq 3$ , etc) will be summarised by dose regimen; events in each category will be further summarised by MedDRA system organ class and preferred term. SAEs will be summarised separately, if a sufficient number occurs.

Adverse event summary tables will include only TEAEs. AEs will be defined as treatment-emergent if they have an onset or worsen (by Investigator report of a change in intensity) during the study treatment or the safety follow-up period (defined as 28 or 42 [+ 14] days after last dose of study treatment) but prior to subsequent cancer therapy. AEs occurring outside this period will only be listed.

During the evaluation of the AE data, a Fusion Pharmaceuticals medically qualified expert will review the list of AEs that were not reported as SAEs and AEs leading to discontinuation. Based on the expert's judgement, significant AEs of particular clinical importance may, after consultation with the Global Patient Safety Physician, be considered other significant adverse events (OAEs) and reported as such in the CSR. A similar review of laboratory/vital signs (pulse and blood pressure)/ECG data will be performed for identification of OAEs. Examples of these could be marked haematological and other laboratory abnormalities, and certain events that lead to intervention (other than those already classified as serious), dose reduction, or significant additional treatment.

Duration of exposure will be summarised.

All safety data including safety laboratory values, vital signs, and ECG data will be listed individually by subject and appropriately summarised. For all laboratory variables that are included in the current version of CTCAE, the CTCAE grade will be calculated. Details of any deaths will be listed for all participants. Graphical presentations of safety data will be presented as appropriate. DLTs will be displayed in a listing.

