5. *Extended Safety Follow-up Period:* Because cumulative radiation exposure may be associated with an increased risk of delayed onset of radiation-induced toxicity, participants will undergo additional safety assessments at 3-month intervals. The Extended Safety Follow-up Period will begin 3 months following the last dose of [Ac]-FPI-2068, and will continue every 3 months for 2 years, then every 6 months for an additional 3 years up to 5 years, or until the participant withdraws from the study (see Section 7.2). Refer to Section 8.1.8 for the assessment details and timepoints performed and for the biospecimens and information collected during the Extended Safety Follow-up Period.

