Prior to the administration of [Ac]-FPI-2068, all AEs related to [In]-FPI-2107 or FPI-2053 should be resolved to Grade 1 or baseline. A delay of 28 days is acceptable from the time of the last [In]-FPI-2107 ( $\pm$  FPI-2053) administration to the administration of [Ac]-FPI-2068 if an AE related to [In]-FPI-2107 or FPI-2053 requires longer time for resolution. In circumstances (e.g., intercurrent illness, etc.) where a delay of [Ac]-FPI-2068 administration may be necessary, the Sponsor and/or Medical Monitor must be consulted to discuss whether the participant can receive [Ac]-FPI-2068. In this scenario, Sponsor and/or Medical Monitor agreement is required prior to [Ac]-FPI-2068 administration. Laboratory results confirming bone marrow and organ function, within retreatment criteria requirements must be documented within 48 hours prior to each cycle of [Ac]-FPI-2068 administration.

Refer to Sections 8.1.4 through 8.1.7 for the assessment details and timepoints performed, and for the biospecimens and information collected during the Treatment Period.

4. *End of Treatment and 28- or 42-Day (+ 14 days) Safety Follow-Up Period:* Participants who do not receive any [Ac]-FPI-2068 (i.e., those who do not enter the Treatment Period) will have a Day 28 ( $\pm$  3 days) safety visit as their last study visit. Participants who receive treatment with [Ac]-FPI-2068 will have a safety visit on Day 42 (+ 14 days) before entering the Extended Safety Follow-up Period.
5. *Extended Safety Follow-up Period:* Because cumulative radiation exposure may be associated with an increased risk of delayed onset of radiation-induced toxicity, participants will undergo additional safety assessments at 3-month intervals. The Extended Safety Follow-up Period will begin 3 months following the last dose of

[Ac]-FPI-2068, and will continue every 3 months for 2 years, then every 6 months for an additional 3 years up to 5 years, or until the participant withdraws from the study (see Section 7.2). Refer to Section 8.1.8 for the assessment details and timepoints performed, and for the biospecimens and information collected during the Extended Safety Follow-up Period.

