### 8.1.8 End of Treatment and Extended Follow-up Period

**Table 25** Schedule of Assessments - End of Treatment and Extended Follow-up Period

Assessments/procedures a	End of Treatment b	42 -Day (+ 14 days) Safety Follow-Up c	Extended Safety Follow-up (after the last dose)	Details in Section/Appendix
	± 3 days	After the last dose (± 3 days)	Every 3 months (± 2 weeks) for 2 years then every 6 months for 3 years	
Subsequent anti-cancer treatment	X	X	X	9.4.2
AE monitoring	X	X	X d	8.5
Concomitant medications and procedures	X	X		6.6
Haematology (whole blood) with blood smear (pathology)	X	X	X	8.4.4
Clinical chemistry (serum or plasma)	X	X	X	8.4.4
Thyroid panel		X		8.4.4
Urinalysis		X		8.4.4
Pregnancy test (blood or urine, in accordance with institutional practice)	X			8.4.4
Complete physical examination	X			8.4.1
Symptom-directed physical examination		X		8.4.1
ECOG Performance Status	X	X		8.4.5
Weight	X			8.4.1
Ophthalmologic examination	X			8.4.6.2
CT or MRI for RECIST 1.1 Response Assessments	X d		X e	8.2
Serum for tumour marker measurement (e.g., CA-19-9, CEA, etc.) g	X		X h	8.8.1.3
Blood for TCR analysis	X		X	8.8.1.1

ADA, anti-drug antibody; AE, adverse event; CA-19-9, carbohydrate antigen-19-9; CEA, carcinoembryonic antigen; CT, computed tomography; ctDNA, circulating tumour DNA; ECOG, Eastern Cooperative Oncology Group; MRI, magnetic resonance imaging; PK, pharmacokinetics; RECIST, Response Evaluation Criteria in Solid Tumours; RNA, ribonucleic acid; TCR, T-cell receptor.

**a** If clinically indicated, any procedure or assessment may be conducted as an unscheduled visit.

**b** The End of Treatment visit should be conducted within 7 days of the decision to permanently discontinue treatment with  $[^{225}\text{Ac}]$ -FPI-2068.

The Follow-up Visits should be scheduled within CSP-defined timeframe (e.g., 42-56 days) based on the date of the last dose of IMP.

d Only related AEs to be collected in the Extended Follow-Up Period.

Only related AEs to be collected in the Extended Follow Up Period.

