#### **8.5.1 Time Period and Frequency for Collecting AE and SAE Information**

Data on AEs and SAEs will be collected from time of signature of the informed consent form, throughout the Treatment Period and including the 28 or 42-day (+ 14 days) safety follow-up

period. During the extended follow-up period, only data for SAEs will be collected.

SAEs will be recorded from the time of signing of the informed consent form.

If the Investigator becomes aware of an SAE with a suspected causal relationship to the IMP that occurs after the end of the clinical study in a participant treated by him or her, the Investigator shall, without undue delay, report the SAE to the Sponsor.

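### The follow-up meant to detect late radiation toxicity has two contradictory AE collection rules, and AEs arising in it can only be listed, not summarised by dose level

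*Protocol*

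**What the plan says.** **Purpose and length of the follow-up.** Section 4.1.4 explains the Extended Safety Follow-up Period by the concern that "cumulative radiation exposure may be associated with an increased risk of delayed onset of radiation-induced toxicity". The Synopsis gives the same reason and the timing: "The Extended Safety Follow-up Period will begin 3 months following the last dose of" [225Ac]-FPI-2068, and visits "will continue every 3 months for 2 years, then every 6 months for an additional 3 years up to 5 years".

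**Collection rule in Section 8.5.1.** "During the extended follow-up period, only data for SAEs will be collected". Relatedness plays no part.

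**Collection rule in Table 25, footnote d (Section 8.1.8).** "Only related AEs to be collected in the Extended Follow-Up Period". Seriousness plays no part.

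**SAE reporting in Section 8.5.9.** Every SAE is to be reported and entered in the eCRF, whether or not it is thought to be caused by the product or a study procedure. Appendix B 2 counts follow-up among the study phases in which an SAE can occur.

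**Analysis in Section 9.4.3.** "Adverse event summary tables will include only TEAEs". An AE is treatment-emergent if it starts or worsens during treatment or within 28 or 42 (+14) days of the last dose, and before any subsequent cancer therapy. For the rest: "AEs occurring outside this period will only be listed".

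**The concern.** Two sites can each follow the protocol and record different events for the same period. A late, related, non-serious AE is recorded at a site that works from Table 25 and not at a site that works from Section 8.5.1. The number of such events would then depend partly on which page a site reads, and no later analysis can recover an event that was never entered.

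Section 9.4.3 adds a second problem. The frequency, duration and severity of AEs are a primary endpoint (Table 6), and the extended period exists to observe delayed toxicity. Yet AEs that begin in that period are kept out of every AE summary table. At stake is a tabulated account, by dose level, of the clinical late toxicity that the follow-up was set up to find.

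**Working it through.** The plan states no figure on this point. The check is a cross-classification of the two rules and date arithmetic on the windows.

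**1. The two collection rules, extended follow-up only**

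| Event | Table 25, footnote d | Section 8.5.1 | Agree? |
|---|---|---|---|
| Related, serious | collected | collected | yes |
| Related, non-serious | collected | not collected | **no** |
| Unrelated, serious | not collected | collected | **no** |
| Unrelated, non-serious | not collected | not collected | yes |

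The rules disagree in 2 of 4 cells. Section 8.5.9 settles one of these elsewhere in the text: unrelated SAEs must be reported. For that cell, footnote d is in conflict with two sections, and the data should still arrive. Nothing else in the protocol settles the related, non-serious cell.

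**2. Can an AE with onset in extended follow-up be treatment-emergent?**

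Inputs:
- Latest close of the window for participants treated with [225Ac]-FPI-2068: 42 + 14 = 56 days after the last dose (Section 9.4.3). It closes sooner if new cancer therapy starts.
- Start of extended follow-up: 3 months after the last dose, 3 × 365.25/12 = 91.3 days (Synopsis; Section 4.1.4).
- Visit tolerance in extended follow-up: ±2 weeks (Table 25).

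Results:
- From the latest close of the window to the start of the period: 91.3 − 56 = 35.3 days.
- Earliest possible first extended visit: 91.3 − 14 = 77.3 days, still later than day 56.
- Visits, counting months from the last dose: 3, 6, …, 24 (8 visits) and 30, 36, …, 60 (6 visits), 14 in all. None falls inside the window.

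An AE with onset in extended follow-up therefore cannot be treatment-emergent, and under Section 9.4.3 it cannot appear in an AE summary table.

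**3. What the window does capture**

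A late effect of an early cycle is still treatment-emergent if it appears before the window closes. With three cycles at the planned 56-day interval, the window runs to 2 × 56 + 56 = 168 days after the first dose; with both intervals extended to 84 days, to 2 × 84 + 56 = 224 days. The exclusion applies to events that begin after that.

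**4. A side observation**

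Between day 56 and about day 91, neither the safety follow-up rule nor the extended follow-up rule plainly applies to AE collection. A reconciled rule should close this gap of about 35 days as well.

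**The case against.** The strongest case on the other side is that late safety data are collected and reported by other routes. Most of it stands, and it rules out several stronger conclusions that a reader might draw.

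- *Late cytopenia or renal decline would never be recorded.* Not supported. Table 25 schedules haematology with blood smear and clinical chemistry throughout extended follow-up, and Table 29 includes serum creatinine and urea nitrogen. What depends on the collection rule is the AE entry and its causality rating.
- *No late toxicity is summarised at all.* Not supported. Section 9.4.3 has safety data, including laboratory values, summarised with CTCAE grades calculated, and Section 9.4.1 presents summaries by cohort or dose level. Neither statement is tied to the treatment-emergent window. Deaths are listed, and an expert review may identify other significant AEs. None of these is an AE summary, and laboratory tables cover neither clinical AEs nor causality.
- *Unrelated late SAEs are lost.* Not supported, because of Section 8.5.9 and Appendix B 2. New cancers (Section 8.5.11) and deaths from late-onset toxicity (Section 8.5.12) are also reportable as SAEs.
- *About 97% of safety time goes untabulated.* The arithmetic, (1826 − 56)/1826 = 0.97, is planned calendar time. It assumes that everyone remains in follow-up for five years, in a population whose eligibility requires a life expectancy of only 3 months or more. Section 4.4 also sets the main data cut-off at the last death or 2 years after the final participant stops treatment, whichever is sooner. The figure is not a measure of what would be lost.
- *Dose decisions would be made without late toxicity.* Not supported. Section 6.7.8 gives the Safety Review Committee all available data during the study, and the table rule in Section 9.4.3 does not restrict that review.

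It can also be said that tabulating treatment-emergent events and listing later ones is common practice, that cohorts of three to nine can be read from a listing, and that the statistical analysis plan could add a table. The first two are fair where late effects are incidental; here they are the stated reason for the follow-up, and backfill cohorts of about 20, possibly about 60, are foreseen. The third does not answer the point: the protocol itself fixes listing only, and an analysis plan cannot repair a collection rule.

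Finally, Section 9.4.3 promises a separate SAE summary if there are enough events. That is conditional, and the treatment-emergent restriction follows in the next paragraph, so it does not clearly bring late SAEs in.

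**Conclusion.** The point holds in two parts. First, Section 8.5.1 and Table 25, footnote d, contradict each other in 2 of 4 event types for the same period. The practical loss falls on related, non-serious late AEs if sites follow 8.5.1; for unrelated SAEs the fault is a conflict between footnote d and Section 8.5.9 rather than a clear loss of data. Second, Section 9.4.3 keeps every AE with onset in extended follow-up out of the AE summaries by dose level and leaves it to a listing.

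This is a wrong rule in the current text, not detail left for later. It should be corrected, but it does not threaten the dose-escalation decisions or the laboratory safety results. How many events are affected cannot be derived from the protocol, which gives no expected rate of late toxicity and no survival assumption. The window calculation rests only on the stated 42 (+14) days and 3 months, with a month taken as 365.25/12 days.

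**What to change.** 1. **Collection.** Put one rule in both Section 8.5.1 and Table 25, footnote d: from the end of the safety follow-up through extended follow-up, collect all SAEs, and all AEs judged related whatever their seriousness. This agrees with Section 8.5.9 and closes the interval before month 3.

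2. **Analysis.** In Section 9.4.3, replace the listing-only rule with a simple summary, by dose level, of related AEs and of SAEs with onset after the treatment-emergent window, in participants who received [225Ac]-FPI-2068. Keep the listing beside it.

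A cumulative incidence with death as a competing event, or a further split by cycles received, is optional; with cohorts this small it would be sparse outside the larger backfill groups.

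**Cost.** Wording in three places, slightly more AE data entry at visits already scheduled, and one extra table. No additional visit and no change to sample size.

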#### **9.4.4 Other Analyses**

##### **9.4.4.1 Pharmacokinetics**

PK analysis of [Ac]-FPI-2068 and [In]-FPI-2107, with and without preadministration of FPI-2053, will be performed on whole blood radioanalysis and serum antibody (total/conjugated) concentrations collected at time points specified in the SoAs.

Where data allow, PK parameters (including but not limited to clearance, AUC,  $C_{max}$ ,  $t_{max}$ , and half-life) will be calculated using non-compartmental analysis using actual sampling times and

standard non-compartmental methods.

All PK concentrations and any derived PK parameters will be listed and summarised. The PK concentrations and parameters listings will be presented for the Safety Analysis Set. PK concentrations and parameters will be summarised using appropriate descriptive statistics for the PK Analysis Set.

Exploratory analyses including potential population PK and/or PK/pharmacodynamics may be described in a separate analysis plan. Where relevant, data collected from this study may be combined with other data from other studies for modelling purposes in the future. All analysis results may be reported separately from the CSR.

#### **9.4.4.2 Biomarkers**

Descriptive statistics of actual and change from baseline will be provided by dose level for exploratory biomarker measurement based on the PK Analysis Set.

#### **9.4.4.3 Immunogenicity**

Immunogenicity results will be analysed descriptively by summarising the number and percentage of participants who develop detectable ADAs. The immunogenicity titre may be reported for samples confirmed positive for the presence of ADAs. The potential impact of ADAs on PK, pharmacodynamics, and safety will be assessed if data allow. Samples confirmed positive for ADAs may also be evaluated for neutralising antibody activity.

### **9.5 Interim Analyses**

No interim analyses are planned for this study.

## **10 SUPPORTING DOCUMENTATION AND OPERATIONAL CONSIDERATIONS**

## Appendix A Regulatory, Ethical, and Study Oversight Considerations

### A 1 Regulatory and Ethical Considerations

- This study will be conducted in accordance with the CSP and with the following:
  - Consensus ethical principles derived from international guidelines including the Declaration of Helsinki and Council for International Organizations of Medical Sciences (CIOMS) International Ethical Guidelines
  - Applicable International Council for Harmonisation (ICH) Good Clinical Practice (GCP) Guidelines
  - Applicable laws and regulations
- The CSP, revised CSP, ICF, Investigator Brochure, and other relevant documents (e.g., advertisements) must be submitted to an IRB/IEC by the Investigator and reviewed and approved by the IRB/IEC before the study is initiated.
- Any revised CSPs will require IRB/IEC and applicable Regulatory Authority approval before implementation of changes made to the study design, except for changes necessary to eliminate an immediate hazard to study participants.
- Fusion Pharmaceuticals will be responsible for obtaining the required authorisations to conduct the study from the concerned Regulatory Authority. This responsibility may be delegated to a CRO but the accountability remains with Fusion Pharmaceuticals.
- The Investigator will be responsible for providing oversight of the conduct of the study at the site and adherence to requirements of 21 CFR, ICH guidelines, the IRB/IEC, European Regulation 536/2014 for clinical studies (if applicable), European Medical Device Regulation 2017/745 for clinical device research (if applicable), and all other applicable local regulations.

### Regulatory Reporting Requirements for SAEs

- Prompt notification by the Investigator to the Sponsor of a SAE is essential so that legal obligations and ethical responsibilities towards the safety of participants and the safety of a study intervention under clinical investigation are met.
- The Sponsor has a legal responsibility to notify both the local regulatory authority and other regulatory agencies about the safety of a study intervention under clinical investigation. The Sponsor will comply with country-specific regulatory requirements relating to safety reporting to the regulatory authority, Institutional Review Boards (IRB)/Independent Ethics Committees (IEC), and Investigators.
- For all studies except those utilising medical devices, Investigator safety reports must be prepared for suspected unexpected serious adverse reactions (SUSAR) according to local regulatory requirements and Sponsor policy and forwarded to Investigators as necessary.

- An Investigator who receives an Investigator safety report describing a SAE or other specific safety information (e.g., summary or listing of SAEs) from the Sponsor will review and then file it along with the IB and will notify the IRB/IEC, if appropriate according to local requirements.

### **Regulatory Reporting Requirements for Serious Breaches**

- Prompt notification by the investigator to the Sponsor of any (potential) serious breach of the protocol or regulations is essential so that legal and ethical obligations are met.
  - A 'serious breach' means a breach likely to affect to a significant degree the safety and rights of a participant or the reliability and robustness of the data generated in the clinical study.
- If any (potential) serious breach occurs in the course of the study, investigators or other site personnel will inform the appropriate Sponsor representatives immediately after he or she becomes aware of it.
- In certain regions/countries, the Sponsor has a legal responsibility to notify both the local regulatory authority and other regulatory agencies about such breaches.
  - Sponsor will comply with country-specific regulatory requirements relating to serious breach reporting to the regulatory authority, IRB/IEC, and investigators. If EU Clinical Trials Regulation 536/2014 applies, Sponsor is required to enter details of serious breaches into the European Medicines Agency CTIS. It is important to note that redacted versions of serious breach reports will be available to the public via CTIS.
- The investigator should have a process in place to ensure that:
  - The site staff or service providers delegated by the investigator/institution are able to identify the occurrence of a (potential) serious breach.
- A (potential) serious breach is promptly reported to Sponsor or delegated party, through the contacts (email address or telephone number) provided by Sponsor.

